#### 1.1.1.1.5 Non Index Lesions

Measurable lesions, other than index lesions, and all sites of non-measurable disease, will be identified as non-index lesions. Non-index lesions will be evaluated at the same assessment time points as the index lesions. In subsequent assessments, changes in non-index lesions will contribute only in the assessment of complete response.

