## 2.1.1 HTLV-1 Associated Adult T-Cell Leukemia Lymphoma

Although HTLV-2 is not clearly associated with a clinical disorder, HTLV-1 is closely associated with two clinical disorders [1]. About 5% of HTLV-1 infected individuals eventually develop a form of myelopathy known as HTLV-1 myelopathy (HAM) or tropical spastic paraparesis (TSP). It is characterized by lower limb spasticity, bowel and bladder disturbances, and slow but steady progression over several years. HTLV-1 has also been associated with other inflammatory clinical conditions, including uveitis, arthropathy, myopathy, pneumopathy, and a Sjogren's disease-like syndrome [8]. Some investigators have suggested that these disorders are related to high virus load, overstimulation of dendritic cells, resulting in chronic production of high levels of type 1 interferons and interferon-stimulated gene expression.

About 5% of HTLV-1 infected individuals develop a T-cell non-Hodgkin's lymphoma designated adult T-cell leukemia lymphoma (ATLL). It occurs almost exclusively in individuals who acquired HTLV-1 as a result of breast feeding, although four or five decades are generally required before development of disease. ATLL is characterized by frequent blood and bone marrow involvement, hypercalcemia, and lytic bone lesions. It is most commonly a CD4+ leukemia/lymphoma, although occasional examples of CD8+ lymphoma have been described. ATLL may fit into a variety of pathological subtypes as classified by the International Working Party Formulation. Clinical classifications of ATLL have included a "smoldering" disorder characterized by rash and minimal blood involvement, as well as a chronic form of ATLL, which have median survivals of two years or more (Fig 1) [9]. In contrast, a "lymphomatous" form of ATLL and an "acute" form of ATLL have median survivals of 3-6 months.

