# 11.1.4 Response Criteria

Response Criteria for Adult T-Cell Leukemia-Lymphoma									
Response	Definition	Lymph Nodes	Extranodal Masses	Spleen, Liver	Skin	Peripheral Blood	Bone Marrow		
Complete Remission 	Disappearance of all disease	Normal	Normal	Normal	Normal	Normal 	Normal		
Uncertified Complete Remission 	Stable residual mass in bulky lesion	$\geq 75\%$ decrease 	$\frac{>75\%}{\text{decrease}^3}$	No increase	≥50% decrease	$\geq 50\%$ decrease	Normal		
Partial Remission 	Regression of disease	$\geq 50\%$ decrease 	$\geq 50\%$ decrease 	No increase	$\geq 50\%$ decrease	$\geq 50\%$ decrease	Irrelevant		
Stable Disease 	Failure to attain complete/partial remission and no progressive disease	No change in size	No change in size	No change in size	No chance in size	No change	No change		
Relapse Disease or Progressive Disease	New or increased lesions	New or $\geq 50\%$ increase 	New or $\geq 50\%$ increase 	New or $\geq 50\%$ increase	New or $\geq 50\%$ increase	New or $\geq 50\%$ increase 	Re- appearance		
Not Assessable									

Require each criterion to be present for a period of at least 4 weeks

 Provided that <5% of flower cells remained, complete remission was judged to have been attained if the absolute lymphocyte count, including flower cells, was  $<4x10^{9}/L$ 

Calculate by the sum of the products of the greatest diameters of measurable disease

 Defined by  $\geq$  50% increase from nadir in the sum of the products of measurable disease

 Defined by  $\geq$ 50% increase from nadir in the count of flower cells and an absolute lymphocyte count, including flower cells, of >4x10^9/L

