#### **13. STATISTICAL CONSIDERATIONS**

#### 13.1 Study Objectives and Endpoints

The primary objective of this study is to determine safety, tolerability, and efficacy of nivolumab for patients with HTLV-associated ATLL. The safety and tolerability will be measured by the frequency of adverse events (AEs) and the number of patients who discontinue therapy due to intolerable toxicity, while the efficacy will be measured as overall response (Complete Response/CR+Partial Response/PR) rate.

The secondary objectives include

- To determine effects of nivolumab on HTLV-1 proviral DNA and RNA loads;
- To determine the effects of nivolumab on anti-HTLV-1 and anti-ATLL immune responses;
- To determine effects of nivolumab on HTLV-1 integration site clonality.

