#### 13.3 Data Analysis

Data analysis of the study will be descriptive in nature. Demographic and clinical characteristics of the sample, toxicity by grade, as well as tumor response, duration of response, and length of follow-up will be summarized using descriptive statistics. Binomial proportions and their 90% confidence intervals will be used to estimate the response rates of therapy. Binomial proportions and their 90% confidence intervals will also be calculated for the efficacy based on immune response criteria (Appendix D). The Kaplan-Meier method will be used to evaluate the response duration. Analysis of variance methods will be used to evaluate the effects of treatment and time on the viral load measurements, as well as measurements of viral transcripts. The incidence of toxicities will be estimated using the binomial proportion and its 90% confidence interval. A proportional hazards analysis with viral load measures as time dependent covariates will be used to evaluate the effects of treatment and structure the effects of these measures on duration of response. Detailed analysis of correlative studies and biomarkers are listed in Section 9.

The safety and tolerability will be monitored every 2 weeks. All patients who receive treatment with nivolumab will be eligible for safety and tolerability analysis. A Bayesian sequential monitoring method [58] will be used for safety analysis and the stopping rule is defined as  $Pr(\theta>0.10 | data)>0.90$ , where  $\theta$  denotes the proportion of patients who discontinue therapy due to intolerable toxicity. That is, enrollment will be stopped early whenever, given the accumulated observed data, there is >90% probability that the discontinuation of therapy is greater than 10%. Specifically, enrollment will be stopped early if 3 patients discontinue therapy in the first 12 patients, or 4 patients discontinue therapy in the first 19 patients, or 5 patients discontinue therapy before the last patient enrolled. These boundaries were obtained using the free-download software Multc99 (version 2.1) from M.D. Anderson Cancer Center. We assume that the parameter  $\theta$ follows a prior distribution of beta ( $\alpha$ ,  $\beta$ ), with  $\alpha$  and  $\beta$  representing the number of patients discontinuing and continuing therapy respectively.

	Ethnic Categories				T ( )
Racial Categories	Not Hispanic or Latino		Hispanic or Latino		Total
	Female	Male	Female	Male	
American Indian/ Alaska Native	0	0	0	0	0

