#### 1.1.1.1.6 Calculation of Sum of Product of Diameters (SPD)

Sum of Product of Diameters is an estimate of tumor burden. The 2 greatest perpendicular diameters are used to estimate the size of each tumor lesion. The SPD is calculated as the sum of the product of the diameters for index tumor lesions. Several variations of the SPD are identified for the purpose of classification of tumor responses.

**SPD at Baseline**: The sum of the product of the diameters for all index lesions identified at baseline prior to treatment on Day 1.

**SPD at tumor assessment**: For every on-study tumor assessment collected per protocol or as clinically indicated, the SPD at tumor assessment will be calculated using tumor imaging scans. All index lesions and all new measurable lesions that have emerged after baseline will contribute to the SPD at tumor assessment (irSPD).

**SPD at NADIR:** For tumors that are assessed more than 1 time after baseline, the lowest value of the SPD (SPD Baseline or SPD at tumor assessment) is used to classify subsequent tumor assessments for each subject. The SPD at tumor assessment using the irRC for progressive disease incorporates the contribution of new measurable lesions. Each net percentage change in tumor burden per assessment using irRC accounts for the size and growth kinetics of both old and new lesions as they appear. In this study the irRC as defined by the Investigator will serve as the basis of key endpoints for efficacy analyses and guide clinical care.

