#### 1.1.1.1.10 Definition of Overall Response Using irRC Will Be Based on the Following Criteria:

- Immune-related Complete Response (irCR): Complete disappearance of all tumor lesions (index and non-index), together with no new measurable or unmeasurable lesions, for at least 4 weeks from the date of documentation of irCR. All lymph nodes short axes must be < 10 mm.
- Immune-related Partial Response (irPR): The sum of the products of the 2 largest perpendicular diameters of all index lesions is measured and captured as the SPD baseline. At each subsequent tumor assessment, the sum of the products of the 2 largest perpendicular diameters of all index lesions and of new measurable lesions are added together to provide the Immune Response Sum of the Product of the Diameters (irSPD). A decrease, relative to baseline of the irSPD of 50% or greater is considered an irPR, in the absence of irCR. Must be confirmed no less than 4 weeks from the first irPR.
- **Immune-related Stable Disease (irSD):** irSD is defined as the failure to meet criteria for immune complete response or immune partial response, in the absence of progressive disease.
- Immune-related Progressive Disease (irPD): It is recommended in difficult cases (eg, increase in SPD or irSPD accompanied with significant individual lesion regression, "mixed response", or in presence of stable or improving performance status/clinical condition) to confirm PD at the following tumor assessment. Any of the following will

constitute progressive disease:

- At least 25% increase in the SPD of all index lesions over nadir SPD calculated for these lesions.
- At least a 25% increase in the SPD of all index lesions and new measurable lesions (irSPD) over the nadir SPD calculated for the index lesions.

Index Lesion Definition	Non Index Lesion Definition	New Measurable Lesions	New Unmeasurable Lesions	% Change in irSPD Tumor Burdon (including measurable new lesions when present)	Overall irRC Response
Complete Response	Complete Response	No	No	-100%	irCR
Partial Response	Any	Any	Any	$\leq -50\%$ >-50% to <+25% $\geq +25\%$	irPR irSD irPD
Stable Disease	Any	Any	Any	-50% to <+25% $\geq$ +25%	irSD irPD
Progressive Disease	Any	Any	Any	≥+25%	irPD

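### The supplementary irRC response rate cannot record a partial response in patients without an index lesion and ignores blood progression in those who have one; its denominator is not stated

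*Combined protocol and SAP*

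**What the plan says.** Section 13.1 defines the efficacy endpoint: "the efficacy will be measured as overall response (Complete Response/CR+Partial Response/PR) rate". Sections 11.1 and 11.1.4 assess it by the ATLL consensus criteria, which have separate columns for nodes, extranodal masses, spleen and liver, skin, blood and marrow. Footnote 5 of that table defines blood progression as a 50% or greater "increase from nadir in the count of flower cells and an absolute lymphocyte count, including flower cells", with the lymphocyte count above 4×10⁹/L.

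Section 13.3 then adds a second rate: "Binomial proportions and their 90% confidence intervals will also be calculated for the efficacy based on immune response criteria (Appendix D". Appendix D defines it as follows.

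- **Partial response:** "A decrease, relative to baseline of the irSPD of 50% or greater is considered an irPR, in the absence of irCR". The irSPD sums index lesions and new measurable lesions.
- **Progression:** an increase of at least 25% over nadir in the same kind of sum.
- **Non-index disease:** "changes in non-index lesions will contribute only in the assessment of complete response". The section on non-index response repeats that such disease does not enter irPR and does not by itself make irPD.
- **Role:** under the SPD calculation, "the irRC as defined by the Investigator will serve as the basis of key endpoints for efficacy analyses".

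Section 3.1 admits acute, lymphoma, chronic and smoldering ATLL. No criterion in 3.1 or 3.2 requires measurable disease. Section 2.1.1 notes that "ATLL is characterized by frequent blood and bone marrow involvement".

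**The concern.** The irRC in Appendix D measure lesions in two diameters. Much of ATLL is not a lesion of that kind: circulating flower cells, marrow infiltration, patches and plaques. The scale treats two groups of patients in a way that a reader of the irRC rate would not expect.

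1. Patients with no index lesion cannot be shown to have a partial response. If they stay in the denominator, they lower the rate for a reason unrelated to drug effect.
2. Patients with an index lesion can be counted as responders while their leukemia progresses. This raises the rate.

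The two errors run in opposite directions, and their balance depends on the subtype mix, so the irRC rate cannot be interpreted without knowing who could be scored. Section 13.3 does not say which patients form its denominator.

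**Working it through.** **The plan's own figure.** The illustration below borrows N = 20 and the 40% rate from 13.2, so I checked that design first. With p0 = 0.10, p1 = 0.40, a stop at 1 or fewer responses in 9, and success at 5 or more in 20:

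P(success | p) = Σ over x = 2 to 9 of P(Bin(9,p) = x) × P(Bin(11,p) ≥ 5 − x).

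This gives 0.0349 at p = 0.10 and 0.9018 at p = 0.40. The probability of stopping early under p0 is 0.7748, so expected N is 9 + 11 × (1 − 0.7748) = 11.48. That is the Simon optimal design for these inputs. The sample size is not in dispute.

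**A patient without an index lesion.** The baseline sum is 0. Percent change is (current − 0)/0, which is undefined, so the 50% decrease needed for irPR cannot be shown. The irRC table has no row for this patient. Because irSD is the residual category, both a clear blood response and blood progression would fall into it. Whether irCR can be scored is also unclear, because the table asks for a −100% change in irSPD.

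**A patient with index lesions and rising leukemia (assumed lesions).**

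- Baseline: 30×20 and 25×20 mm, sum 600 + 500 = 1,100.
- Later: 18×12 and 16×12 mm, sum 216 + 192 = 408.
- Change: 408/1,100 − 1 = −62.9%.

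Once confirmed at 4 weeks or later, this is irPR whatever the blood shows. If flower cells have also doubled and lymphocytes exceed 4×10⁹/L, 11.1.4 calls the same patient progressive.

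**Which denominator.** Three sections could apply.

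| Section | Patients counted |
|---|---|
| 11.1.1 | Measurable disease at baseline, at least one cycle, re-evaluated |
| 13.2 | All who received study medication |
| 13.4.2 | All eligible patients, possibly except those never treated |

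Section 11.1.1 does not match Appendix D exactly either. Under 11.1.2 one diameter of 10 mm on CT is enough. Appendix D needs two diameters (20 and 10 mm, or 10×10 mm on spiral CT). A 12×8 mm non-nodal lesion on spiral CT is measurable under the first and not under the second.

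**Size under the wide denominators.** Assume that k of 20 patients have no index lesion, that 40% of the others respond by irRC, and that the k patients get no irRC response. The rate is 0.40 × (20 − k)/20.

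| k | Expected irRC rate |
|---|---|
| 0 | 40% |
| 2 | 36% |
| 4 | 32% |
| 6 | 28% |
| 8 | 24% |
| 10 | 20% |

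The documents do not give k. If irCR could be scored without an index lesion, and a quarter of a 40% response rate were complete (a further assumption), k = 6 would give 0.7 × 40% + 0.3 × 10% = 31% instead of 28%. If 11.1.1 set the denominator, there would be no loss from this source. In the other direction, each patient scored irPR despite blood progression adds 1/20 = 5 points.

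**The case against.** The strongest reply is that 13.3 describes its analyses as descriptive, attaches no decision rule to the irRC rate and plans no formal comparison with the primary rate. The primary criteria already cover skin, blood and marrow. Section 11.1.1 can also be read as limiting response evaluation to patients with measurable disease, which is close to the fix proposed here. All of this is fair and limits the point to a supplementary estimate. It does not remove the point, because 13.2 and 13.4.2 lead to a wider denominator and 13.3 chooses none of the three.

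Several stronger readings are tempting, but the documents do not support them.

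- **Skin-only patients can never be irPR.** Appendix D does not exclude skin tumors measurable in two diameters, and 11.1.3 and Appendix C provide for clinical measurement of skin lesions. Against this, the SPD section takes on-study sums from imaging. The documents are unclear; they do not rule such patients out.
- **Patients without an index lesion can never progress.** New measurable lesions enter irSPD and can arguably give irPD, although a percentage over a zero nadir is undefined.
- **The irRC ignore non-measurable disease altogether.** irCR requires all non-index lesions to disappear.
- **A doubling of flower cells alone is progression under 11.1.4.** Footnote 5 also requires the lymphocyte threshold.
- **Any blood, skin or marrow progression should cancel an irRC response.** A new skin lesion is progression in 11.1.4, whereas Appendix D says new lesions alone are not. A full override would replace the irRC with a debatable hybrid.

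**Conclusion.** The concern holds for the supplementary irRC rate. Appendix D cannot show irPR in a patient without an index lesion, and it counts a patient with shrinking index lesions as a responder even when the blood meets 11.1.4 progression. Under the wide denominators the first effect lowers a 40% rate to between 36% and 20% for 2 to 10 unscorable patients of 20. That range rests on an assumed share and on giving those patients no irRC response. The second effect adds 5 points per patient, and the number of such patients is also unknown.

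A reader might infer that the primary response rate is biased too, because Appendices C and D say that the investigator bases response, and key endpoints, on the irRC. The endpoint and design sections do not support this: 11.1 and 11.1.4 assign response to the ATLL criteria, and 13.3 presents the irRC rate as an addition. The statements do conflict, however, and should be reconciled.

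**What to change.** In 13.3 and Appendix D:

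1. Calculate the irRC rate and its 90% interval only in patients with at least one index lesion at baseline, and state that N. Assess the others by 11.1.4 only.
2. Report a cross-table of irRC response against 11.1.4 response that identifies irPR and irCR patients with blood, marrow or skin progression by 11.1.4. This shows the discordance without redefining either scale.
3. State whether clinically measured skin tumors enter the SPD, reconciling 11.1.3, the photography section of Appendix C and the measurable-lesion definition in Appendix D with the imaging wording of the SPD section.
4. Reconcile the Appendix C and D statements on the role of the irRC with 11.1 and 11.1.4.

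The cost is a few sentences. Blood counts with differential and SWAT scores are already scheduled. Marrow entries will be sparser, because the study calendar ties repeat marrow to a complete response by all other criteria. The statistical cost is precision: at a fixed response proportion, interval width grows roughly as √(20/n), so n = 14 gives √(20/14) ≈ 1.20, about 20% wider than with 20 patients.

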#### 1.1.1.1.6 Calculation of Sum of Product of Diameters (SPD)

Sum of Product of Diameters is an estimate of tumor burden. The 2 greatest perpendicular diameters are used to estimate the size of each tumor lesion. The SPD is calculated as the sum of the product of the diameters for index tumor lesions. Several variations of the SPD are identified for the purpose of classification of tumor responses.

**SPD at Baseline**: The sum of the product of the diameters for all index lesions identified at baseline prior to treatment on Day 1.

**SPD at tumor assessment**: For every on-study tumor assessment collected per protocol or as clinically indicated, the SPD at tumor assessment will be calculated using tumor imaging scans. All index lesions and all new measurable lesions that have emerged after baseline will contribute to the SPD at tumor assessment (irSPD).

**SPD at NADIR:** For tumors that are assessed more than 1 time after baseline, the lowest value of the SPD (SPD Baseline or SPD at tumor assessment) is used to classify subsequent tumor assessments for each subject. The SPD at tumor assessment using the irRC for progressive disease incorporates the contribution of new measurable lesions. Each net percentage change in tumor burden per assessment using irRC accounts for the size and growth kinetics of both old and new lesions as they appear. In this study the irRC as defined by the Investigator will serve as the basis of key endpoints for efficacy analyses and guide clinical care.

#### 1.1.1.1.7 Definition of Index Lesion Response

**Immune-related Complete Response (irCR),** which is defined as complete disappearance of all index lesions. Lymph nodes that shrink to < 10 mm short axis are considered normal.

**Immune-related Partial Response (irPR),** which is defined as a decrease, relative to baseline, of 50% or greater in the sum of the products of the 2 largest perpendicular diameters of all index and all new measurable lesions (ie, Percentage Change in Tumor Burden), in the absence of irCR.

Note: the appearance of new measurable lesions is factored into the overall tumor burden, but does not automatically qualify as progressive disease until the SPD increases by  $\geq 25\%$  when compared to SPD at nadir

Immune-related Stable Disease (irSD), which is defined as not meeting the criteria for irCR or

irPR, in the absence of immune-related progressive disease (irPD)

**Immune-related Progressive Disease (irPD),** which is defined as at least a 25% increase in Tumor Burden (ie, taking sum of the products of all index lesions and any new measurable lesions) when compared to SPD at nadir.

#### 1.1.1.1.8 Definition of Non-Index Lesion Response

**Immune-related Complete Response (irCR),** which is defined as complete disappearance of all non-index lesions. Lymph nodes that shrink to < 10 mm short axis are considered normal.

**Immune-related Partial Response (irPR),** non-index lesion(s) are not considered in the definition of PR, this term does not apply.

**Immune-related Stable Disease (irSD),** non-index lesion(s) are not considered in the definition of SD, this term does not apply.

**Immune-related Progressive Disease (irPD),** increases in number or size of non-index lesion(s) does not constitute progressive disease unless/until Tumor Burden increases by 25% (ie, the SPD at nadir of index lesions and any new measurable lesions increases by the required amount).

#### **1.1.1.1.9** Impact of New Lesions on irRC

New lesions alone do not qualify as progressive disease. However their contribution to total tumor burden is included in the SPD which in turn feeds into the irRC for tumor response. Therefore, new non-measurable lesions will not discontinue any subject from the study.

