## 5.5 Criteria for Removal from Study

Patients will be removed from study when any of the criteria listed in Section 5.3 applies. The reason for study removal and the date the patient was removed must be documented in the Case Report Form.

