#### 5.8 Treatment Beyond Progression

Patients are allowed to continue treatment for 4-6 weeks and reassessed. Treatment may continue up to an additional 30% total single diameter increased over baseline, if no change in performance status, no new serious adverse event, and no need for intervention. New measureable lesions are not permitted with this schema.

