advised. However, such techniques may be useful to confirm complete pathological response when biopsies are obtained or to determine relapse in trials where recurrence following complete response (CR) or surgical resection is an endpoint.

Tumor markers alone cannot be used to assess response. If markers are initially above the upper normal limit, they must normalize for a patient to be considered in complete clinical response.

Cytology, Histology: These techniques can be used to differentiate between partial responses (PR) and complete responses (CR) in rare cases (*e.g.*, residual lesions in tumor types, such as lymphoma, where known residual benign tumors can remain).

The cytological confirmation of the neoplastic origin of any effusion that appears or worsens during treatment when the measurable tumor has met criteria for response or stable disease is mandatory to differentiate between response or stable disease (an effusion may be a side effect of the treatment) and progressive disease.

FDG-PET While FDG-PET response assessments need additional study, it is sometimes reasonable to incorporate the use of FDG-PET scanning to complement CT scanning in assessment of progression (particularly possible 'new' disease). New lesions on the basis of FDG-PET imaging can be identified according to the following algorithm:

- a. Negative FDG-PET at baseline, with a positive FDG-PET at follow-up is a sign of PD based on a new lesion.
- b. No FDG-PET at baseline and a positive FDG-PET at follow-up: If the positive FDG-PET at follow-up corresponds to a new site of disease confirmed by CT, this is PD. If the positive FDG-PET at follow-up is not confirmed as a new site of disease on CT, additional follow-up CT scans are needed to determine if there is truly progression occurring at that site (if so, the date of PD will be the date of the initial abnormal FDG-PET scan). If the positive FDG-PET at follow-up corresponds to a pre-existing site of disease on CT that is not progressing on the basis of the anatomic images, this is not PD.

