#### 1.1.1.1.3 Non-Measurable Lesions

Non-measurable (evaluable) lesions are all other lesions, including unidimensional measurable disease and small lesions (lesions without at least 1 diameter  $\geq 20$  mm, or pathological lymph nodes with short axis  $\leq 15$  mm), and any of the following: lesions occurring in a previously irradiated area (unless they are documented as new lesions since the completion of radiation therapy), bone lesions, leptomeningeal disease, ascites, pleural or pericardial effusion, lymphangitis cutis/pulmonis, abdominal masses that are not pathologically/cytologically confirmed and followed by imaging techniques and cystic lesions. Lymph nodes that have a short axis < 10 mm are considered non-pathological and should not be recorded or followed.

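### The plan does not say whether a new non-measurable lesion is progression: Section 11.1.4 says yes, Appendix D says no, and no rule of precedence connects them to Sections 5.3, 5.5 and 5.8

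*Combined protocol and SAP*

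**What the plan says.** **Appendix D (irRC).** Under Impact of New Lesions: "New lesions alone do not qualify as progressive disease", and then "Therefore, new non-measurable lesions will not discontinue any subject from the study". Neither sentence carries a condition or a time limit. Progression needs a rise in measured burden: "At least a 25% increase in the SPD of all index lesions and new measurable lesions (irSPD) over the nadir SPD". The non-measurable class includes "bone lesions, leptomeningeal disease, ascites, pleural or pericardial effusion". The section on calculating the sum of products of diameters (SPD) makes investigator-assessed irRC the basis of key efficacy endpoints and a guide to care. Appendix C also has the investigator judge response by irRC.

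**Section 11.** Section 11.1 assigns both response and progression to the ATLL consensus criteria. Section 11.1.4 defines progression as "New or increased lesions" and does not separate measurable from non-measurable new lesions. Section 11.1.3 adds: "Negative FDG-PET at baseline, with a positive FDG-PET at follow-up is a sign of PD based on a new lesion". It also requires cytology of a new or worsening effusion, when measurable tumor is responding or stable, to tell response or stable disease from progression.

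**Treatment and study status.** The Schema continues therapy until progression, and Section 5.3 lists progression among the events that end treatment. Section 5.5: "Patients will be removed from study when any of the criteria listed in" Section 5.3 applies. Section 5.8 allows 4-6 weeks of treatment beyond progression with reassessment, and conditional continuation after that, but "New measureable lesions are not permitted with this schema".

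**Analysis.** Section 13.3 reports an irRC response rate in addition to the main one.

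**The concern.** The Appendix D sentence does more than classify a scan: it says who stays on the study. For a patient whose only change is a new non-measurable lesion, it gives a different answer from Section 11.1.4 read with Sections 5.3 and 5.5. The event is plausible in this disease, since Section 2.1.1 names lytic bone lesions as a feature of ATLL and Appendix D classes bone lesions as non-measurable.

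Three endpoints depend on the progression date. Best overall response (11.1.4.1) counts responses only until progression. Duration of response (11.1.5) ends there, and PFS (11.1.6) uses it as an event. With about 20 patients and a decision boundary of 5 responders, one patient classified differently can change the conclusion. Sites also lack a single instruction on whether such a patient continues treatment.

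**Working it through.** **1. The rules applied to one event.** Assume index lesions of 40 x 30 mm and 25 x 20 mm, unchanged, plus one new non-measurable lesion.

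- SPD at baseline = 1200 + 500 = 1700 mm². SPD at the visit = 1700 mm². Change = 0%, below the 25% threshold.
- Appendix D: immune-related stable disease (irSD), no progression date, patient not discontinued.
- Section 11.1.4: progression, dated to this visit. Sections 5.3 and 5.5 then end treatment and remove the patient.
- Section 5.8: the lesion is not measurable, so the bar does not apply. Treatment may continue for 4-6 weeks with reassessment, and conditionally after that.

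Section 5.8 narrows the gap without closing it. It is limited and conditional where Appendix D is neither, and Sections 5.3 and 5.5 do not refer to it.

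**2. A new measurable lesion.** Assume the index SPD falls from 4000 to 2400 mm² (-40%) and a new 16 x 18 mm node appears. The node is measurable, as its short axis is at least 15 mm.

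- irSPD = 2400 + 16 x 18 = 2688 mm².
- Change from baseline = 2688/4000 - 1 = -32.8%.
- irRC progression is judged from nadir. If the nadir is 2400, the change is 2688/2400 - 1 = +12%, so irSD. Because 2688/1.25 = 2150.4, irSD holds only if the nadir exceeds about 2150 mm².
- Section 11.1.4 gives progression, and Section 5.8 does not permit the lesion.

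**3. The design as stated.** Section 13.2 stops at 1 or fewer responders in 9 and declares efficacy at 5 or more in 20, with a null rate of 10% and an alternative of 40%. By exact enumeration:

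P(declare | p) = sum over x = 2 to 9 of P(X1 = x) x P(X2 ≥ 5 - x), with X1 ~ Bin(9, p) and X2 ~ Bin(11, p).

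- p = 0.10: 0.0349.
- p = 0.40: 0.902.

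The stated 5% one-sided error and 90% power are met.

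**4. One extra responder at the final count.** If a response after a new lesion is counted, a trial with 4 responders reaches 5. Keep the interim rule and replace 5 - x by 4 - x:

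- p = 0.10: 0.0911.

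The documents give no frequency for a new lesion followed by qualifying shrinkage. Let f be the assumed share of trials in which one extra responder is gained this way:

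false-positive probability = 0.0349 + f x (0.0911 - 0.0349)

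| Assumed f | Probability at a true 10% rate |
|---|---|
| 0 (as designed) | 3.5% |
| 10% | 4.1% |
| 25% | 4.9% |
| 50% | 6.3% |
| 100% | 9.1% |

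**The case against.** The strongest reply is that the plan already assigns these endpoints. Section 11.1 gives response and progression to the ATLL criteria. Best overall response, duration and PFS are all defined within that section, and Section 13.3 treats irRC as an addition. Response is reviewed by an independent expert (11.1.7), and the interim analysis uses independent review (13.2), so site classification need not decide the count. This reply would succeed if Appendix D were only a supplementary tabulation. But Appendix C bases the investigator's response assessment on irRC, and Appendix D makes irRC the basis of key endpoints and a guide to care. Independent review does not say which criteria the reviewer should use for progression.

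Some stronger readings are not supported:

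- A reader might infer that the patient is both on and off therapy. Section 5.8 allows some treatment after progression and bars only new measurable lesions, so the instructions overlap for a time. Section 5.3 also lets the investigator stop when the patient's condition makes treatment unacceptable, and Section 5.2.1 takes patients who need chemotherapy or radiation off treatment. Appendix D therefore does not force continuation.
- A reader might infer two progression dates. For this event irRC gives none; a later date arises only if the irSPD afterwards rises 25% from nadir. A separate irRC result is partly intended.
- A reader might infer that removal ends participation. Section 5.4 follows patients for 1 year after removal.
- The site columns in 11.1.4 name no CNS, bone or effusion category. For those sites, progression rests on the general definition and on 11.1.3.

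**Conclusion.** The contradiction is in the text, and the plan should resolve it. A new non-measurable lesion alone is progression on that date under Section 11.1.4, and irSD with no progression date under Appendix D. No passage sets precedence. New measurable lesions raise a related conflict: Section 5.8 does not permit them, while Appendix D does not treat them as progression until the burden rises 25% from nadir.

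The firm statement of size is that one patient with a new lesion followed by qualifying shrinkage can move 4/20 to 5/20. The probability range of 4.1% to 9.1% rests on assumed frequencies and a fixed interim rule. A reader might take 9.1% as the trial's error rate, but it requires an extra responder in every null trial. Up to an assumed 25% of trials, the probability stays below the 5% design level. Duration of response and PFS are also affected, by an amount the documents do not allow one to estimate.

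**What to change.** **Treatment and study status.** The Schema, Sections 5.3, 5.5, 5.8, 11.1, 11.1.3 and 11.1.4, the image acquisition text of Appendix C, and the Appendix D text on SPD, index-lesion response and new lesions must be reconciled. The result should be one statement of what a new measurable or non-measurable lesion does to treatment and study status, cross-referred from 5.3, 5.5, 5.8 and Appendix D. Which clinical rule is right is not for this review to say.

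**Analysis, whichever disposition is chosen.** State that, for best overall response, duration of response and PFS, a new lesion meeting 11.1.4 is recorded as progression on the date first documented, consistent with Section 11.1. Use irRC only for the additional tabulation in Section 13.3, and align the statements on the role of irRC in Appendices C and D with this.

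**Cost.** Protocol wording and one CRF instruction. No new assessments or patients are needed.
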